#### **9.1.2. Interim Analyses for Futility**

##### **9.1.2.1. Simon 2-Stage Futility Rules**

An interim analysis of efficacy will be conducted in Phase 2 by applying the Simon 2-stage design for each tumor within a given treatment group. During Stage 1,  $n_1$  evaluable subjects treated at the recommended dose and schedule will be enrolled, and if  $r_1$  or fewer responses (Table 2) are observed by the Week 16 assessment, then the cohort will be discontinued. To be counted as evaluable for the calculation in Stage 1, subjects must have discontinued from the study, reached the Week 16 assessment, or had at least 2 scans. As discussed in Section 3.2, the Simon 2-stage designs conducted for each tumor type within each treatment group have design parameters that are determined by historical response rates and will have different sample sizes and futility results depending on the historical response rate.

As an example, the probability of early termination for Stage 1 in the SCCHN tumor cohort for the doublet combination of INCAGN01876 and nivolumab in Treatment Groups F, G, and H is

summarized in [Table 11](#). If at least 4 responses (CR or PR) are observed in the first evaluable 16 subjects, then 30 additional evaluable subjects will be enrolled in this cohort for Stage 2.

[figure not shown]
Per mRECIST v1.1, the tumor response should be confirmed by a repeat radiographic assessment not less than 4 weeks from the date that the first response was documented. Disease progression will be confirmed by a second tumor assessment in at least 4 weeks and no later than 6 weeks after the first scan indicating PD in clinically stable subjects. The first tumor assessment is conducted in the eighth week. If a CR or PR occurs after an unconfirmed PD in at least 4 weeks but no more than 6 weeks, then the tumor assessment will be counted as a corresponding CR or PR (Section [7.3.2.3](#)).

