7.7. Efficacy Assessments

7.7.1. Modified RECIST v1.1 Assessment Disease

Modified RECIST will be applied by the site as the primary measure for assessment of tumor response and as a basis for Protocol guidelines related to disease status (eg, discontinuation of study therapy). As noted in Section 1.5.4.1, RECIST v1.1 has been adapted to account for the unique tumor responses seen with immunotherapy (Wolchok et al 2009).

If radiologic imaging shows progressive disease, tumor assessment should be repeated at a minimum of 4 weeks, but no later than 6 weeks later to confirm progression, with the option of continuing treatment while awaiting radiologic confirmation of progression. Table 13 provides instructions on how to proceed with treatment based on the subject's clinical status once the initial scan showing radiologic evidence of progression is observed.

Subjects may receive treatment while waiting for confirmation of progression if they are clinically stable as defined by the following criteria:

- Absence of clinically significant signs and symptoms (including worsening of laboratory values) indicating disease progression.
- No decline in ECOG performance status.
- Absence of rapid progression of disease.
- Absence of progressive tumor at critical anatomical sites (eg, cord compression) requiring urgent alternative medical intervention.

Table 13: Imaging and Treatment After First Radiologic Evidence of Progressive Disease

	Clinically Stable		Clinically Unstable	
	Tumor Imaging	Treatment	Tumor Imaging	Treatment
First radiologic evidence of progression	Repeat imaging 4-6 weeks to confirm progression	May continue study treatment at the investigator's discretion while awaiting confirmatory tumor imaging	Repeat tumor imaging 4-6 weeks to confirm progression per physician discretion only	Discontinue treatment
Repeat scan confirms progression	No additional tumor imaging required	Discontinue treatment	No additional tumor imaging required	N/A
Repeat scan shows SD, PR, or CR	Continue regularly scheduled tumor imaging assessments	Continue study treatment at the investigator's discretion	Continue regularly scheduled tumor imaging assessments	May restart study treatment if condition has improved and/or clinically stable per investigator's discretion

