**Table 2: Planned Simon 2-Stage Designs for Phase 2**

Indication	Treatment Groups	$r_1$	$n_1$	$r$	$n_2$	$n$	$p_0$	$p_1$
SCCHN	F, G, H	3	16	10	30	46	15%	35%
Gastric	F, G, H	3	16	10	30	46	15%	35%
Endometrial	F, G, H	4	17	14	34	51	20%	40%
SCHHN	J, K, L	5	18	17	32	50	25%	45%
Gastric	J, K, L	5	18	17	32	50	25%	45%
Endometrial	J, K, L	7	21	19	27	48	30%	50%

- $r_1$ : if  $r_1$  or fewer responses are observed during Stage 1, the study cohort is stopped early for futility.
- $n_1$ : number of subjects initially enrolled in Stage 1.
- $n_2$ : number of subjects enrolled in Stage 2.
- $r$ : if  $r$  or fewer responses are observed by the end of Stage 2, then no further investigation of the drug combination is warranted in the selected tumor type and dosing schedule.
- $n$ : total number of subjects.
- $p_0$ : insufficient response rate.
- $p_1$ : target response rate.

In Phase 2 of the study, toxicities will continue to be monitored. If the cumulative incidence of Grade 3 to 5 INCAGN01876-related AEs occurs in > 40% of subjects in a particular treatment group after 6 subjects have been enrolled, then further enrollment in that treatment group will be interrupted until the sponsor, investigators, and regulatory authorities (if applicable) determine the appropriate course of action (eg, lower the dose of INCAGN01876, change dose frequency, etc). If a treatment group is discontinued due to toxicity, it may be re-initiated at a previously tested lower dose level and/or alternate dosing schedule. All AEs, regardless of the time of occurrence on study, may be considered for DLT determination purposes.

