### 3.3. Control of Type I Error

For the primary efficacy endpoints, the 1-sided Type I error will be controlled at 0.05 for each individual cohort expansion. Note that this level of significance does not account for the multiple expansion cohorts. For other endpoints, CIs will be reported at a 95% confidence level.

During the Phase 1 portion of the study, telephone conferences will be scheduled by the sponsor with study investigators in order to review cohort-specific data and overall safety data, to agree on dose escalation, adjudicate individual high-grade AEs as potentially dose-limiting, and guide other major study decisions. An internal DMC will be assembled to monitor safety data and

study conduct on a regular and ongoing basis during the Phase 2 portion of the study. See Section 9 for details regarding the interim analyses conducted in this study.

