In order to determine whether the target response rate ( $p_1$ ) is likely, an initial number of evaluable subjects ( $n_1$  subjects) treated at the MTD or PAD and schedule of INCAGN01876 within the corresponding doublet or triplet expansion cohort will be enrolled in a cohort (Stage 1). If there are  $r_1$  or fewer responses in the cohort, it will be concluded that the true response rate is unlikely to be greater than or equal to the target rate, and no more subjects will be enrolled in that tumor type in Stage 2. In the cohorts in which greater than  $r_1$  responses are observed among the Stage 1 subjects,  $n_2$  additional evaluable subjects will be treated in Stage 2 to estimate the response rate. At the end of Stage 2, if  $\leq r$  subjects have responded among the  $n$  evaluable subjects, the doublet or triplet schedule will be declared nonpromising for that cohort. In other words, after the study is finished, if there is a sufficient number of responses in the 2 stages combined, the study doublet or triplet is considered promising; otherwise it is considered nonpromising. The detailed calculations for each tumor type-specific doublet and triplet cohort are based on a 1-sided Type I error of 0.05 and power of 85%. The individual  $p_0$  and  $p_1$  values for the tumor types within doublet or triplet expansion cohorts are listed in [Table 2](#). [Table 2](#) shows that there are 4 unique Simon 2-Stage designs: the Simon 2-stage designs for gastric and SCCHN within the INCAGN01876 + nivolumab cohorts use the same assumptions as the Simon 2-stage designs for gastric and SCCHN within the INCAGN01876 + nivolumab + ipilimumab cohorts. [Figure 2](#) shows the power to reject the null hypothesis under various response rates for the 4 unique Simon 2-stage designs, in which each line of the figure represents the power for a unique Simon 2-stage design.

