#### **7.3.2. Objective Response Rate and Best Overall Response**

##### **7.3.2.1. Confirmed ORR and Confirmed BOR by RECIST v1.1**

Per RECIST v1.1, in nonrandomized studies where response is the primary endpoint, confirmation of PR and CR is required to ensure responses are not the result of measurement error. Therefore, a subject is defined as a confirmed objective responder if the subject has an overall response of CR or PR at any postbaseline visit that is confirmed at a subsequent timepoint at least 4 weeks later, before the first occurrence of PD. Confirmed objective responders will be assessed based on RECIST v1.1.

Confirmed ORR is defined as the proportion of subjects with confirmed overall responses. Confirmed ORR will be estimated with 95% CIs. Confidence intervals will be based on the method for Simon 2-stage CIs of response rates outlined in Koyama and Chen (2008).

Confirmed ORR will be summarized by treatment group and tumor type as primary endpoint for the Phase 2 response evaluable population.

In general, confirmed BOR is the best response recorded postbaseline before and including the first PD, in the order of CR, PR, SD, PD and NE, in which CR and PR must be confirmed at a subsequent timepoint at least 4 weeks after the CR or PR is observed. Responses of CR, PR, or SD after the first assessment of PD will not be considered. In the case of SD, measurements must meet the SD criteria at least once after the date of first dose at a minimum interval of 49 (56 – 7) days. Subjects who fail to meet this criterion will have confirmed BOR of PD if the next available assessment indicates PD or NE if there is no additional assessment available.

Under RECIST v1.1, if radiologic imaging shows CR or PR, a tumor assessment should be repeated at a minimum of 4 weeks to confirm the response in order to claim the CR or PR as the confirmed BOR. If there is no second CR or PR tumor assessment, the CR or PR will be unconfirmed. Table 4 lists the scenarios of responses that can occur after an unconfirmed CR or PR and provides a rule for determining the confirmed BOR in each scenario. A sensitivity analysis for the ORR, in which BOR is determined using unconfirmed PR and CR, is detailed in Section 7.3.2.2.

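### The Stage 1 futility count in SAP 9.1.2.1 is not defined the way the primary endpoint is, so the stated 0.05 and 85% are not established for the rule as written

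*SAP*

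**What the plan says.** **Stage 1 look (SAP 9.1.2.1).** Each cohort enrolls n1 evaluable subjects. If r1 or fewer responses "are observed by the Week 16 assessment, then the cohort will be discontinued". The stopping sentence and the SCCHN example name no response criteria. A later paragraph of the same section describes only mRECIST v1.1, with confirmation at least 4 weeks later, and adds a counting rule: "If a CR or PR occurs after an unconfirmed PD in at least 4 weeks but no more than 6 weeks", the assessment is taken as that CR or PR.

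**Primary endpoint (SAP 7.1 and 7.3.2.1).** This is ORR per RECIST v1.1. The response must be confirmed at least 4 weeks later and before first progression. The section also says: "Responses of CR, PR, or SD after the first assessment of PD will not be considered". It sets no calendar limit on when a response may first appear or be confirmed.

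**Which endpoint the Simon rule belongs to.** The text beside SAP Table 11 presents the early-termination probabilities as those for the primary endpoint, and Protocol 9.4.1.1 sets out r1 and r under ORR per RECIST v1.1. Protocol 7.7.1, on the other hand, says: "Modified RECIST will be applied by the site as the primary measure for assessment of tumor response".

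**Stated operating characteristics.** In SAP 3.4.2 the designs are "based on a 1-sided Type I error of 0.05 and power of 85" percent. SAP 3.3 adds that "the 1-sided Type I error will be controlled at 0.05 for each individual cohort expansion".

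**The concern.** The error rates of a Simon design assume that the count compared with r1 at Stage 1 is part of the count compared with r at the end. Here the two counts can differ in two ways.

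- **Look-only responses.** A CR or PR 4 to 6 weeks after an unconfirmed PD is counted in the Stage 1 section but never in the primary ORR. If unconfirmed responses are accepted at the look, those that are never confirmed fall in the same class. A cohort could continue on responses that the primary analysis discards.
- **Late responses.** A response first seen after Week 16 counts only at the end. If the look requires confirmation by Week 16, a response first seen at Week 16 is lost to it as well. An active cohort could be closed while responses are pending.

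Because r1 or fewer responses leads to closure, two statisticians following the same SAP could count the same Stage 1 data differently and reach opposite decisions.

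**Working it through.** **1. Timing.** Protocol 7.7.1.1.2 schedules scans 8 weeks after first dose and every 8 weeks after that: Weeks 8, 16, 24. A response first seen at Week 16 can be confirmed no earlier than Week 16 + 4 = 20, or at Week 24 on the regular schedule.

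**2. Reproducing the plan.** The designs are in SAP Table 2 and Protocol Table 19; for the SCCHN doublet the row reads "SCCHN F, G, H 3 16 10 30 46 15% 35"%. The cervical cohorts in the protocol use the endometrial designs of the SAP, and melanoma appears in the protocol only. With X1 ~ Bin(n1, p) and X2 ~ Bin(n2, p):

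- Early termination = P(X1 ≤ r1).
- Rejection probability = Σ over x > r1 of P(X1 = x) · P(X2 ≥ r + 1 − x), giving alpha at p0 and power at p1.

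For r1 = 3 and n1 = 16, early termination is 0.7899, 0.5981, 0.4050, 0.2459 and 0.1339 at true rates of 15, 20, 25, 30 and 35%. This matches Table 11. With one endpoint at both looks, alpha is 0.043 to 0.049 and power 0.850 to 0.854 in the five distinct two-stage designs, so the stated figures reproduce.

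**3. Adding a mismatch.** The documents give no discordance rates, so these are assumptions:

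- m = share of eventual confirmed RECIST responders who cannot be counted at Stage 1.
- e = proportion of subjects counted at Stage 1 who are not confirmed RECIST responders.

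Each Stage 1 subject falls in one of four classes: countable responder, p(1 − m); late responder, pm; look-only, e; neither, 1 − p − e. The cohort continues if countable + look-only > r1. It succeeds if countable + late + X2 > r. Exact multinomial results, alpha / power:

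| Design | e=0, m=0 | m=10% | m=20% | e=5 points | e=5 points, m=10% | e=5 points, m=20% |
|---|---|---|---|---|---|---|
| SCCHN/gastric doublet | 0.0486 / 0.8506 | 0.0403 / 0.7807 | 0.0316 / 0.6871 | 0.0589 / 0.9095 | 0.0525 / 0.8686 | 0.0452 / 0.8080 |
| Cervical doublet | 0.0487 / 0.8541 | 0.0396 / 0.7756 | 0.0301 / 0.6673 | 0.0576 / 0.9099 | 0.0506 / 0.8642 | 0.0424 / 0.7926 |
| Relapsed melanoma | 0.0482 / 0.8535 | 0.0435 / 0.8137 | 0.0378 / 0.7557 | 0.0535 / 0.8884 | 0.0509 / 0.8709 | 0.0476 / 0.8431 |
| SCCHN/gastric triplet | 0.0430 / 0.8500 | 0.0353 / 0.7719 | 0.0266 / 0.6559 | 0.0483 / 0.8929 | 0.0427 / 0.8495 | 0.0355 / 0.7742 |
| Cervical triplet | 0.0471 / 0.8502 | 0.0375 / 0.7647 | 0.0263 / 0.6271 | 0.0520 / 0.8846 | 0.0453 / 0.8411 | 0.0360 / 0.7538 |

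Look-only responses can only raise alpha and power; late responses can only lower both.

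**4. Ceiling on alpha.** If the look never stopped a cohort, alpha would be P(Bin(n, p0) > r): 0.0745, 0.0707, 0.0579, 0.0551 and 0.0570 in table order.

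The calculation covers the two-stage Simon rule only. It does not cover the integrated Bayesian rule or the three-stage PD-1 refractory SCCHN design.

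**The case against.** A reader might infer that the Stage 1 look has been switched to mRECIST and that the 0.05 and 85% therefore fail. The documents support neither statement.

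- The sentence containing r1 does not name mRECIST, and the mRECIST paragraph does not name r1. The remark beside Table 11 and Protocol 9.4.1.1 both point to RECIST v1.1. What stands is a conflict within the documents, not a demonstrated change of endpoint.
- The cut-off wording refers to responses observed, not confirmed, by Week 16. The loss of a response first seen at Week 16 depends on the stricter reading. Under that reading look-only responses would be rare: a PD at Week 8 followed by a response at Weeks 12 to 14 could be confirmed only at Weeks 16 to 18. Under the looser reading, responses first seen after Week 16 are still missed.
- Every discordance rate is assumed, and offsets are possible. With 2 points of look-only responses and 5% late, the SCCHN/gastric doublet gives 0.0495 and 0.8525, so both stated figures hold.
- Protocol Amendment 5 says that enrollment is complete, so a change can no longer alter which cohorts were closed.

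These points limit the claim. They do not remove the conflict: a stopping rule should name one response definition, and this one can be read two ways.

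**Conclusion.** The concern holds in this form: the Stage 1 count and the primary endpoint differ in the criteria described, in the handling of responses after progression and in the time window, and the documents disagree about which definition governs r1. The stated 1-sided 0.05 and 85% are correct for one endpoint at both looks, but they are not established for the rule as written.

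The size depends on rates the documents do not give. Late responses matter more: at 10% late with no look-only responses, power is 0.76 to 0.81 across designs, and at 20% it is 0.63 to 0.76. The alpha effect is modest: 0.048 to 0.059 at 5 points look-only, and never above 0.0745. With both present, the stated figures may be missed in either direction or roughly met. At 5 points and 10%, the SCCHN/gastric doublet has 0.0525 and 0.87, and the SCCHN/gastric triplet 0.043 and 0.85.

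**What to change.** In SAP 9.1.2.1:

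- Define a Stage 1 response as in SAP 7.3.2.1: confirmed per RECIST v1.1, none after first PD.
- Count a response first documented by Week 16 once a later scan confirms it.
- Do not declare futility while pending confirmations could lift the count above r1.
- Remove the mRECIST counting paragraph from this section.

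These changes alone do not secure 85% power, because responses first seen after Week 16 would still count only in the final ORR. Either use all available follow-up for the n1 subjects at the look, or state that the 85% assumes every response is first documented by Week 16.

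Reconcile the wording of Protocol 7.7.1 with RECIST v1.1 as the primary endpoint criterion. Since enrollment is complete, record which definition each Stage 1 decision used and report the Stage 1 counts under the primary definition.

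**Cost.** A SAP revision and a clarification in the protocol; n, r1 and r are unchanged. Applied at a live look, the decision could wait about 4 to 8 weeks, only when pending confirmations could change it, or longer if all follow-up is used.

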**Table 11: Probability of Early Termination of Stage 1 for Simon 2-Stage Design of SCCHN in Treatment Groups F, G, and H**

True Response Rate	Probability of Early Termination at Stage 1
15%	79.0%
20%	59.8%
25%	40.5%
30%	24.6%
35%	13.4%

[Table 11](#) provides the probabilities of early termination at the end of Simon Stage 1 for various response rates with regard to the efficacy analysis of the primary endpoint for the 4 unique Simon 2-stage designs given in [Table 2](#). Each line in [Figure 3](#) represents the probability of early termination for a unique Simon 2-stage design.

**Figure 3: Probabilities of Early Termination for Futility at the End of Simon Stage 1 for All Simon 2-Stage Designs Based on Various Assumed Rates of Response to a Given Dose Level**

#### 9.1.2.2. Integrated Bayesian Futility Analysis

In Phase 2, individual cohorts will be closed for futility depending on the results of an integrated Bayesian analysis in which the pooling model requires a priori specification of 2 parameters: the probability of correlation among the cohorts  $\lambda$  and the common probability of activity in the cohorts  $\gamma$ . The integrated Bayesian analysis will be performed each time a subject with endometrial, gastric, or head and neck cancer enters screening. Data will be pooled from cohorts with a common dose sequencing strategy and from cohorts with a common tumor type, with  $\lambda$  and  $\gamma$  specified separately for pooling within the 2 strategies. The pooled model will produce a posterior PoS calculation for each cohort based on pooling within dose sequencing strategy, denoted by PoS1, and pooling within tumor type, denoted by PoS2. PoS is defined as the probability that the ORR for the cohort is greater than or equal to the target response rate,  $p_1$ , from the Simon 2-stage design for the cohort. The PoS calculations are adapted from Simon et al (2016).

The futility rule will stop enrollment in a tumor-sequence pair  $(i, j)$  if both  $PoS1_{ij}$  or  $PoS2_{ij}$  are  $< 20\%$  with the possibility to re-open after more data has accrued and subsequent posterior PoS values are  $\geq 20\%$  for the tumor-sequence pair.

For the futility analyses, we specify  $\lambda = 0.4$  and  $\gamma=0.4$  for pooling within the tumor types and  $\lambda = 0.4$  and  $\gamma = 0.4$  for pooling within the sequencing strategies. In other words, a priori, the correlation between cohorts within the same tumor type and same dose sequencing strategy is assumed to be 40%, and all cohorts within the same tumor type and same dose sequencing strategy are assumed to have a 40% probability of activity.

Further details regarding the Bayesian methodology can be found in Simon et al (2016) and in the technical report in [Appendix B](#).

[Table 12](#) shows the dose sequencing strategy and tumor-type specific strategy for each of the 18 cohorts used for pooling in the integrated Bayesian analysis. Each cell in the table contains a number 1 to 3 representing the dose sequencing strategy and a number 4 to 9 representing the tumor type and treatment information. For pooling within dose sequencing strategy, all cohorts with a common dose sequencing number will be pooled. For pooling within the tumor types, all cohorts with a common tumor type number will be pooled. For example, for pooling within the concurrent dosing sequence, all cohorts with representative cells in the table containing a 1 will be pooled. For pooling within the tumor type strategy of gastric within INCAGN01876 + nivolumab, all cohorts with representative cells in the table containing a 5 will be pooled.

**Table 12: Bayesian Pooling Strategy by Tumor Type and Sequencing Strategy**

Dosing Schedule	Tumor Types Within Treatment Group		
	Endometrial	Gastric	SCCHN
Treatment Group F	1, 4	1, 5	1, 6
Treatment Group G	2, 4	2, 5	2, 6
Treatment Group H	3, 4	3, 5	3, 6
Treatment Group J	1, 7	1, 8	1, 9
Treatment Group K	2, 7	2, 8	2, 9
Treatment Group L	3, 7	3, 8	3, 9

- 1 = Concurrent dosing
- 2 = Run-in only dosing
- 3 = Run-in + concurrent dosing
- 4 = Endometrial within 1876 + Nivo
- 5 = Gastric within 1876 + Nivo
- 6 = SCCHN within 1876 + Nivo
- 7 = Endometrial within 1876 + Nivo + Ipi
- 8 = Gastric within 1876 + Nivo + Ipi
- 9 = SCCHN within 1876 + Nivo + Ipi

[Table 13](#) provides the operating characteristics for 1000 simulated clinical trials under the global null hypothesis, under which none of the 18 cohorts are active. The table summarizes the expected sample size, expected number of false rejections, and the probability of at least 1 false positive result (family wise error rate) for the integrated Bayesian analysis. For comparison purposes, the table summarizes the expected sample size, and expected number false rejections

for 18 separate Simon 2-stage designs in which the cohorts are stopped for futility according to only the Simon 2-stage rules. In the integrated Bayesian analysis, a cohort can be stopped for futility if either PoS1 or PoS2 is not  $\geq 20\%$  or because the cohort does not meet the response rate requirement of the Simon 2-stage rule at Stage 1. From the table, under the global null hypothesis and certain enrollment assumptions, the integrated Bayesian analysis will result in 22% fewer subjects on average.

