9.6.2. Integrated Bayesian Futility Analysis

A second approach to determining whether the treatment is active or not across the cohorts will use an integrated Bayesian analysis of tumor and dosing strategies based on [Simon et al \(2016\)](#). The integrated Bayesian analysis will be used for the cervical cancer, gastric cancer, and SCCHN cohorts. Pooling is performed within dosing strategies and tumor types to determine if INCAGN01876 is active within any of the given dosing strategies, given tumor types, or given dosing strategy-tumor type combinations. The first Bayesian pooling analysis will allow sharing of information within a tumor type across dosing strategies based on a joint Bayesian prior. The joint Bayesian prior incorporates the unacceptable and target response rates from the Simon 2-stage designs with a parameter indicating the prior probability of homogeneity within the tumor types, which controls the degree of information sharing. A separate analysis will allow sharing of information for dosing strategies across tumor types using a separate joint Bayesian prior. For this analysis, the joint Bayesian prior incorporates the unacceptable and target response rates from the Simon 2-stage designs with a parameter indicating the prior probability of homogeneity within the dosing strategies, which controls the degree of information sharing.

Each time a subject with the tumor type of interest is enrolled, two PoS calculations will be performed using the evaluable subjects: the PoS in tumor type (tumor type_i and dosing strategy_j), PoS_{1ij}, and PoS within dosing strategy (tumor type_i and dosing strategy_j), PoS_{2ij}.

Based on the results of the 2 calculated posterior PoS values, a tumor-sequence pair (_{i,j}) will be considered open for enrollment if and only if either PoS_{1ij} ≥ 20% or PoS_{2ij} ≥ 20%. Otherwise the tumor-sequence pair will be suspended.

At the end of the study, overall PoS tests will be performed using both PoS_{1ij} and PoS_{2ij}. A tumor-sequence strategy will be considered successful if either PoS_{1ij} or PoS_{2ij} > 80%.

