**Table B1: Example PoS Calculations for 3 Stratum**

Stratum	1	2	3
Responders/evaluable subjects	6/20	3/10	1/5
PoS based on $\lambda = 0.5$ and $\gamma = 0.33$	0.99	0.98	0.90
PoS based on $\lambda = 0.05$ and $\gamma = 0.33$	0.99	0.93	0.18

For the purposes of this analysis, we will specify a single value for  $\lambda$  and  $\gamma$ , so that the rate of sharing within sequences and tumor types will be equal, and the prior PoS assumed within strata in the pooling strategies will be equal. The PoS in tumor type (tumor type  $i$  and sequencing strategy  $j$ ) will be denoted by  $PoS1_{ij}$ , and the PoS within sequencing strategy (tumor type  $i$  and sequencing strategy  $j$ ) will be denoted by  $PoS2_{ij}$ .

Based on the results of the 2 calculated posterior PoS values, a tumor-sequence pair ( $i, j$ ) will be considered open for randomization if either  $PoS1_{ij}$  or  $PoS2_{ij}$  is greater than 20%. Otherwise, the tumor-sequence pair will be suspended with the possibility of being re-opened after more data have accrued and subsequent posterior PoS values are greater than 20% for the tumor-sequence pair.

At the end of the study, overall PoS tests will be performed using both  $PoS1_{ij}$  and  $PoS2_{ij}$ . A tumor-sequence strategy will be considered successful at the end of the study if either  $PoS1_{ij}$  or  $PoS2_{ij} > 80\%$ .

Each time a subject with the tumor type of interest is enrolled, 2 PoS calculations will be performed using the evaluable subjects: the PoS in tumor type (tumor type  $i$  and sequencing strategy  $j$ ),  $PoS1_{ij}$ , and PoS within sequencing strategy (tumor type  $i$  and sequencing strategy  $j$ ),  $PoS2_{ij}$ .

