### Simulations and Operating Characteristics

Computer simulations were conducted in R to compare the operating characteristics of the Bayesian basket trial design with the operating characteristics of 18 separate Simon 2-Stage designs. We investigated 6 scenarios that would represent different configurations of null and alternative hypotheses (corresponding to inactivity of drug and activity of drug) within the sequencing strategies and tumor types. For the global null hypothesis of no activity in any cohort (Scenario 1), 2500 replications were performed. All other scenario results were simulated using 1000 replications.

In the computer simulations, we assumed the prior probability of correlation between cohorts within tumor types and sequencing strategies to be  $\lambda = 0.4$  and prior probability of activity to be  $\gamma = 0.4$ .

The Simon 2-Stage designs used in the simulations are given in [Table 2](#). The  $p_1$  and  $p_0$  values are assumed not to change with sequencing strategy. For example, for each of the 3 sequencing strategies tested on the SCCHN doublet,  $p_1 = 0.35$  and  $p_0 = 0.15$ . The total sample sizes if each cohort reached full enrollment are given by the  $n$  column in [Table 2](#).

Within the simulations, a tumor-sequence pair  $(i, j)$  was stopped if neither  $PoS1_{ij}$  nor  $PoS2_{ij}$  was  $\geq 20\%$  at any point. In addition, the first stage rule for the Simon 2-stage design was also applied where enrollment was halted unless more than  $r_1$  of the first  $n_1$  subjects responded to treatment within a tumor-sequence pair. The method rejected the null hypothesis of no activity in a cohort at the end of the study if either  $PoS1_{ij}$  or  $PoS2_{ij} > 80\%$ .

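### SAP 9.1.2.2, in the text introducing Table 13, closes a cohort when either PoS is below 20%, while Protocol 9.6.2 and the rest of the SAP close it only when both are

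*SAP*

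**What the plan says.** **Closing rule.**
- Protocol 9.6.2: a pair "will be considered open for enrollment if and only if either" PoS is at least 20%; otherwise it is suspended. This is recalculated each time a relevant subject enrolls.
- SAP 9.1.2.2, rule statement: enrollment stops if both values are below 20% (the sentence joins the two values with *or* after *both*).
- SAP Appendix B, text after Table B1: a pair "will be considered open for randomization if either" PoS exceeds 20%.
- SAP Appendix B, Simulations and Operating Characteristics: a pair "was stopped if neither" PoS was at least 20% at any point.
- SAP 9.1.2.2, text after Table 12: "a cohort can be stopped for futility if either PoS1 or PoS2 is not" at least 20%.

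**Consequence of closing.** The Protocol Synopsis says *terminated*. Protocol 9.6.2 and SAP Appendix B say *suspended*. SAP 9.1.2.2 stops the pair "with the possibility to re-open after more data has accrued and subsequent posterior PoS values are" at least 20%. Appendix B has parallel wording: "subsequent posterior PoS values are greater than 20% for the tumor-sequence pair".

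**Replicates under the global null.** SAP 9.1.2.2 says that Table 13 "provides the operating characteristics for 1000 simulated clinical trials under the global null hypothesis". Appendix B says that for that scenario "2500 replications were performed".

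**Execution.** Protocol 7.2 has the IRT close a group when the PoS for a combination is below the threshold. It does not say one value or both.

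**The concern.** Not (A ≥ 20% or B ≥ 20%) is the same as both below 20%. Not (A ≥ 20% and B ≥ 20%) is the same as at least one below 20%. The text introducing Table 13 states the second; the other rule statements listed above state the first. The second is stricter, because a cohort doing poorly in one pool would be closed even when the other pool supports it.

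The rule shuts cohorts to assignment through the IRT, and Tables 13 and B3 are its only stated operating characteristics. If someone configured the IRT from that sentence, or judged a cohort closure against it, the closure would be set against operating characteristics simulated under a different rule. A cohort closed on one low value could also be reported as inactive when the Protocol's rule would have kept it open.

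**Working it through.** **1. Table 13 and Table B3 are the same simulation.** Table 13 shows 355.2, 0.0876, 0.104, 457.2 and 0.9. The global-null row of Table B3 shows the same five figures. The rule stated in Appendix B for the simulations therefore applies to Table 13.

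**2. The Simon comparator reproduces.** For each Table 2 design, expected N under p0 is n1 + (1 − PET) × n2, where PET is the probability of r1 or fewer responses in n1. This gives 25.22 (endometrial doublet), 22.30 (gastric and SCCHN doublets, each), 28.48 (endometrial triplet) and 27.04 (gastric and SCCHN triplets, each). With three sequences per design the unrounded total is 457.17, against 457.2 published. The saving is 1 − 355.2/457.2 = 22.3%, against 22% published. The 355.2 itself cannot be reproduced closely, because the SAP does not fully specify how closed cohorts are handled.

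**3. Replicate count.** 0.0876 × 2500 = 219, a whole number of trials. 0.0876 × 1000 = 87.6, which is not. The printed result belongs to 2500 replicates.

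**4. The two rules can disagree.** The posterior comes from the Appendix B prior, including its added terms for the all-active and all-inactive rows, with λ = γ = 0.4. For cohort j let

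L_j = (p1/p0)^r × ((1 − p1)/(1 − p0))^(n − r), and A_j = 1 − γ + γL_j.

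Summing over the 2^k configurations gives

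PoS_i = [(1 − λ) γ L_i ∏_{j≠i} A_j + λγ ∏L_j] / [(1 − λ) ∏A_j + λ(1 − γ + γ ∏L_j)].

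Take illustrative data with 10 evaluable subjects in each cohort used. SCCHN in Group F has 2 responses; SCCHN in Groups G and H have 1 each. The other concurrent cohorts have 4 (endometrial F), 4 (gastric F), 5 (endometrial J), 4 (gastric J) and 4 (SCCHN J).

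*Pooled by tumor* (SCCHN F, G, H; p0 = 0.15, p1 = 0.35):
- L = 0.6367, 0.2087, 0.2087; A = 0.8547, 0.6835, 0.6835; ∏A = 0.3992; ∏L = 0.0277.
- Numerator: 0.6 × 0.4 × 0.6367 × 0.6835² + 0.16 × 0.0277 = 0.0714 + 0.0044 = 0.0758.
- Denominator: 0.6 × 0.3992 + 0.4 × (0.6 + 0.4 × 0.0277) = 0.2395 + 0.2444 = 0.4840.
- PoS for SCCHN-F = **0.157**.

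*Pooled by sequence* (six concurrent cohorts, each with its own p0 and p1 from Table 2):
- L = 2.848 (endometrial F), 5.928 (gastric F), 0.637 (SCCHN F), 2.391 (endometrial J), 1.633 (gastric J), 1.633 (SCCHN J); ∏A = 10.79; ∏L = 68.50.
- Numerator: 0.6 × 0.4 × 0.6367 × (10.79/0.8547) + 0.16 × 68.50 = 1.93 + 10.96 = 12.89.
- Denominator: 0.6 × 10.79 + 0.4 × (0.6 + 0.4 × 68.50) = 6.48 + 11.20 = 17.67.
- PoS for SCCHN-F = **0.729**.

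Protocol 9.6.2 keeps this cohort open because 0.729 ≥ 0.20. The sentence introducing Table 13 closes it because 0.157 < 0.20.

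**5. Design the tables describe.** SAP Table 12 has endometrial, gastric and SCCHN in Groups F, G, H, J, K and L: 3 × 6 = 18 cohorts, three per tumor pool. The current Protocol (Table 5, 9.6.2) applies the analysis to cervical, gastric and SCCHN in F, H, J and L: 3 × 4 = 12 cohorts, two per tumor pool. The SAP (05 DEC 2017) is based on Amendment 2. Amendment 3 (18 DEC 2017) removed endometrial and Groups G and K from Phase 2.

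**The case against.** The best reply is that this is a slip for *neither … is at least 20%* in one descriptive sentence. Appendix B states the simulated closing rule outright, Protocol 9.6.2 is explicit, and the Synopsis refers the reader to the full Protocol. Nothing shows that the IRT used the stricter rule, and Amendment 5 records that enrollment is complete. All of that stands, and it is why the point is minor. The sentence still sits in the operative futility section of the SAP and states a rule that can reverse a decision.

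A reader might infer more in three directions, and the documents do not support it.

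*That the closing rule behind the tables cannot be determined.* It can: Table 13 is the null row of Table B3, and Appendix B gives the rule for that simulation.

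*That re-opening needs both values above 20%,* from the plural *values* in SAP 9.1.2.2 and Appendix B. Neither place says both. The plural can mean successive recalculations, and the Protocol's if-and-only-if condition, re-evaluated at each enrollment, already means that one value is enough.

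*That re-simulating Appendix B would show which re-opening rule was used, or exclude permanent stopping.* It does not. Two reconstructions, differing in details that the SAP leaves open (such as whether enrollment pauses at n1), give null expected N of 378 and 405 for closing on both with re-opening on either, and 300 and 325 for closing on both permanently. The published value is 355.2. The reconstructions differ by 25 to 27 subjects under the same rule, too much to separate the alternatives. The words *at any point* in Appendix B could also be read as permanent stopping.

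**Conclusion.** The sentence introducing Table 13 is wrong as written: it states an either-value closing rule where Protocol 9.6.2, the SAP's own rule statement and Appendix B require both. Its replicate count is wrong too (1000 for 2500). The Synopsis's *terminated* conflicts with *suspended* in Protocol 9.6.2 and Appendix B. The textual and replicate-count points rest on the documents alone. The 0.157 and 0.729 rest on λ = γ = 0.4, the Appendix B posterior and invented interim data in the SAP's 18-cohort layout. They show that the two rules can conflict, not how often they would.

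Severity is minor. No effect on any cohort is shown, and none should be assumed. Whether a closure was made under the Protocol rule is a question for the IRT configuration. Separately, neither table gives operating characteristics for the 12-cohort design now in the Protocol, and correcting the sentence will not change that.

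**What to change.** - SAP 9.1.2.2, text introducing Table 13: say that a cohort can be stopped if both PoS1 and PoS2 are < 20%, and give 2500 null replicates.
- SAP 9.1.2.2, rule statement: replace *or* with *and* after *both*.
- Protocol Synopsis: replace *terminated* with *suspended*.
- SAP 9.1.2.2 and Appendix B: align the re-open wording with Protocol 9.6.2, so that a pair re-opens when either PoS is at least 20%.
- Add a sentence saying that Tables 13 and B3 describe the superseded 18-cohort design (endometrial; Groups G and K), not the current one.
- Confirm that the IRT ran the Protocol 9.6.2 rule. If it did not, report closures under the rule actually run.

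The cost is wording in a few places and one configuration check. These corrections need no new data and no new simulation.
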